#### **8.3.4. Electronic Diary for Reactogenicity: Substudy A and Substudy B**

Participants will be required to complete a reactogenicity e-diary through an application installed on a provisioned device or on the personal device of the participant. All participants will be asked to monitor and record local reactions, systemic events, and antipyretic medication usage for 7 days from the day of administration of the study intervention. The reactogenicity e-diary allows recording of these assessments only within a fixed time window, thus providing the accurate representation of the participant's experience at that time. Data on local reactions and systemic events reported in the reactogenicity e-diary will be transferred electronically to a third-party vendor, where they will be available for review by investigators and the Pfizer clinicians, at all times, via an internet-based portal.

At intervals agreed to by the vendor and Pfizer, these data will be transferred electronically into Pfizer's database for analysis and reporting. Generally, these data do not need to be reported by the investigator in the CRF as AEs. However, if a participant withdraws because of events reported in the e-diary, the event(s) should be recorded on the AE page of the CRF, regardless of whether the investigator considers the event(s) to be clinically significant. If a participant missed reporting an event in the e-diary and reports it to the study site instead, the event should also be recorded on the AE page of the CRF.

Investigators (or designee) will be required to review the reactogenicity e-diary data online at frequent intervals to evaluate participant compliance and as part of the ongoing safety review.

The investigator or designee must obtain stop dates from the participant for any ongoing local reactions, systemic events, or use of antipyretic medication on the last day that the reactogenicity e-diary was completed. The stop dates should be documented in the source documents and the information entered in the CRF.

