#### Assessment of Intensity

The investigator will make an assessment of intensity for each AE and SAE reported during the study and assign it to 1 of the following categories:

- **Mild:** A type of AE that is usually transient and may require only minimal treatment or therapeutic intervention. The event does not generally interfere with usual ADL.
- **Moderate:** A type of AE that is usually alleviated with additional specific therapeutic intervention. The event interferes with usual ADL, causing discomfort, but poses no significant or permanent risk of harm to the research participant.
- **Severe:** A type of AE that interrupts usual ADL, or significantly affects clinical status, or may require intensive therapeutic intervention.

GRADE	If required on the AE page of the CRF, the investigator will use the adjectives MILD, MODERATE, SEVERE, or LIFE-THREATENING to describe the maximum intensity of the AE. For purposes of consistency, these intensity grades are defined as follows:	
1	MILD	Does not interfere with participant's usual function.
2	MODERATE	Interferes to some extent with participant's usual function.
3	SEVERE	Interferes significantly with participant's usual function.

4	LIFE-THREATENING	Life-threatening consequences; urgent intervention indicated.
---	------------------	---

An event is defined as “serious” when it meets at least 1 of the predefined outcomes as described in the definition of an SAE, NOT when it is rated as severe.

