3.1.1.1. Local Reactions

The local reactions assessed and reported in the e-diary are redness, swelling, and pain at the injection site, from Day 1 through Day 7 after the study vaccination, where Day 1 is the day of the study vaccination. The e-diary entries from the participant and unplanned clinical assessments within 7 days after vaccination will be the primary data source for these events. In addition, any AEs recorded on the AE CRF that are considered local reactions within 7 days after vaccination will be consolidated with e-diary data and included in the reactogenicity report. This section describes derivations with details for the assessment of local reactions: presence, severity level, duration, and onset day.

Presence or Absence

For each local reaction and any local reaction on any day, Table 6 explains the algorithm to derive the presence of a reaction (yes or no) during the interval from Day 1 through Day 7, where Day 1 is the day of the study vaccination.

Table 6. Derived Variables for Presence of Each and Any Local Reaction Within 7 Days for the Study Vaccination

Variable	Yes (1)	No (0)
Presence of each local reaction on any day.	Participant reports the reaction as “yes” on any day (Day 1 through Day 7).	Participant reports the reaction as “no” on all 7 days (Day 1 through Day 7) or as a combination of “no” and missing on all 7 days (Day 1 through Day 7).
Presence of any local reaction on any day.	Participant reports any local reaction as “yes” on any day (Day 1 through Day 7).	For all 3 local reactions, participant reports “no” on all 7 days (Day 1 through Day 7) or as a combination of “no” and missing on all 7 days (Day 1 through Day 7).

Note: Completely missing reactogenicity data will not be imputed. Participants with no reactogenicity data reported will not be included in the reactogenicity summaries.

Severity and Maximum Severity

Redness and swelling will be measured and recorded in measuring device units (range: 1 to 21) and then categorized during analysis as absent, mild, moderate, or severe based on the grading scale in Table 7. Measuring device units can be converted to centimeters according to the following formula: 1 measuring device unit = 0.5 cm. Pain at the injection site will be assessed by the participant as absent, mild, moderate, or severe according to the grading scale in Table 7.

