For events recorded in the AE CRF that are considered local reactions and consolidated with e-diary data, the severity will be based on the AE intensity grade recorded in the CRF.

Table 7. Local Reaction Grading Scale

	Mild (Grade 1)	Moderate (Grade 2)	Severe (Grade 3)	Potentially Life-Threatening (Grade 4)^a
Pain at the injection site	Does not interfere with activity	Interferes with activity	Prevents daily activity	Emergency room visit or hospitalization for severe pain
Redness	>2.0 cm to 5.0 cm (5 to 10 measuring device units)	>5.0 cm to 10.0 cm (11 to 20 measuring device units)	>10 cm (≥21 measuring device units)	Necrosis or exfoliative dermatitis
Swelling	>2.0 cm to 5.0 cm (5 to 10 measuring device units)	>5.0 cm to 10.0 cm (11 to 20 measuring device units)	>10 cm (≥21 measuring device units)	Necrosis

a. Only an investigator or medically qualified person is able to classify a reaction as Grade 4; therefore, a confirmed Grade 4 reaction should be reported as an AE in the CRF.

If a Grade 3 local reaction is reported in the reactogenicity e-diary, a telephone contact should occur to ascertain further details and determine whether a site visit is clinically indicated. Only an investigator or medically qualified person is able to classify a participant's local reaction as Grade 4. If a participant experiences a confirmed Grade 4 local reaction, the investigator must immediately notify Pfizer and report it in the designated CRF as Grade 4. A Grade 4 reaction will also be collected as an AE on the CRF. The event will be graded using the AE intensity grading scale.

For each local reaction reported after the study vaccination, the maximum severity grade will be derived for the e-diary collection period (Day 1 through Day 7, where Day 1 is the day of the study vaccination) as follows:

Maximum severity grade = highest grade (maximum severity) within 7 days after administration (Day 1 through Day 7) among severity grades reported for that local reaction.

If a local reaction is captured in more than 1 data source, eg, e-diary, unplanned assessment, and/or the AE CRF, the highest grade (maximum severity) across all sources will be used in the summary.

Duration (First to Last Day Reported)

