3.1.1.2. Systemic Events

The systemic events assessed and recorded in the e-diary are fatigue/tiredness, headache, chills, vomiting, diarrhea, new or worsened muscle pain, and new or worsened joint pain within 7 days after the study vaccination. The e-diary entries from the participant and unplanned clinical assessments within 7 days after vaccination will be the primary data source for these events. In addition, any AEs recorded on the AE CRF that are considered systemic events starting within 7 days after vaccination will be consolidated with e-diary data and included in the reactogenicity report. The derivations for systemic events will be handled similar to the way local reactions are handled for presence of the event, severity level, duration, and onset day (see [Section 3.1.1.1](#)).

The symptoms will be assessed by the participant as absent, mild, moderate, or severe according to the grading scale in Table 8 and recorded in the e-diary. For events recorded in the AE CRF that are considered systemic events and consolidated with e-diary data, the severity will be based on the AE intensity grade recorded in the CRF.

If a Grade 3 systemic event is reported in the reactogenicity e-diary, a telephone contact should occur to ascertain further details and determine whether a site visit is clinically indicated. Only an investigator or medically qualified person is able to classify a participant's systemic event as Grade 4. If a participant experiences a confirmed Grade 4 systemic event, the investigator must immediately notify Pfizer and report it in the designated CRF as Grade 4. A Grade 4 systemic event will also be collected as an AE on the CRF. The event will be graded using the AE intensity grading scale,

Table 8. Systemic Event Grading Scale

	Mild (Grade 1)	Moderate (Grade 2)	Severe (Grade 3)	Potentially Life-Threatening (Grade 4)^a
Vomiting	1-2 times in 24 hours	>2 times in 24 hours	Requires IV hydration	Emergency room visit or hospitalization for hypotensive shock
Diarrhea	2 to 3 loose stools in 24 hours	4 to 5 loose stools in 24 hours	6 or more loose stools in 24 hours	Emergency room visit or hospitalization for severe diarrhea
Headache	Does not interfere with activity	Some interference with activity	Prevents daily routine activity	Emergency room visit or hospitalization for severe headache

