Temperature will be measured and recorded to 1 decimal place. Temperatures recorded in degrees Fahrenheit will be programmatically converted to degrees Celsius for reporting. Temperatures $< 35.0^{\circ}\text{C}$ ($< 95.0^{\circ}\text{F}$) and $> 42.0^{\circ}\text{C}$ ($> 107.6^{\circ}\text{F}$) will be excluded from the analysis. Fever will be grouped into ranges for the analysis according to Table 9.

If a fever of $\geq 39.0^{\circ}\text{C}$ ($\geq 102.1^{\circ}\text{F}$) is reported in the reactogenicity e-diary, a telephone contact should occur to ascertain further details and determine whether a site visit is clinically indicated. Only an investigator or medically qualified person is able to confirm a participant's fever as $> 40.0^{\circ}\text{C}$ ($> 104.0^{\circ}\text{F}$). If a participant experiences a confirmed fever $> 40.0^{\circ}\text{C}$ ($> 104.0^{\circ}\text{F}$), the investigator must immediately notify Pfizer and report it in the designated CRF as fever $> 40.0^{\circ}\text{C}$ ($> 104.0^{\circ}\text{F}$). Fevers $> 40.0^{\circ}\text{C}$ ($> 104.0^{\circ}\text{F}$) will also be collected as an AE on the CRF and assessed by the investigator using the AE intensity grading scale. If a fever is reported in the AE CRF within 7 days after vaccination and no temperature was captured in the CRF, the fever will be included in the reactogenicity summary with “unknown” for temperature range.

Table 9. Scale for Fever

$\geq 38.0\text{--}38.4^{\circ}\text{C}$ ($100.4\text{--}101.1^{\circ}\text{F}$)
$> 38.4\text{--}38.9^{\circ}\text{C}$ ($101.2\text{--}102.0^{\circ}\text{F}$)
$> 38.9\text{--}40.0^{\circ}\text{C}$ ($102.1\text{--}104.0^{\circ}\text{F}$)
$> 40.0^{\circ}\text{C}$ ($> 104.0^{\circ}\text{F}$)

If a systemic event is captured in more than 1 data source, eg, e-diary, unplanned assessment, and/or the AE CRF, the highest grade (maximum severity) across all sources will be used in the summary.

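### In Substudies A and B, redness, swelling, vomiting and diarrhea taken from the AE page are graded on a different scale from the same events in the e-diary, but share the same severity rows

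*SAP*

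**What the plan says.** The relevant rules are in sections 3.1.1.1 and 3.1.1.2 of the SAP for Substudies A and B.

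- **Pooling.** E-diary entries and unplanned clinical assessments are the main source. AE-CRF records judged to be local reactions in the first 7 days "will be consolidated with e-diary data and included in the reactogenicity report". Section 3.1.1.2 does the same for systemic events.
- **Grade of pooled records.** For local reactions that come from the AE page, section 3.1.1.1 states that "the severity will be based on the AE intensity grade recorded in the CRF". Section 3.1.1.2 repeats the rule: it opens "For events recorded in the AE CRF that are considered systemic events and consolidated with e-diary data" and names the same grade source.
- **Grade of e-diary records.** Table 7 bands redness and swelling by measured size. Table 8 bands diarrhea by stools per day, and vomiting by episodes per day with IV hydration as Grade 3.
- **What AE intensity means.** In Protocol 10.3.3 the numbered Grades 1 to 3 rest on interference with usual function, and Grade 4 on life-threatening consequences. The bulleted definitions add need for treatment and, for severe events, effect on clinical status. For mild events they say: "The event does not generally interfere with usual ADL".
- **How a solicited event reaches the AE page.** Protocol 8.3.4 gives one route: "If a participant missed reporting an event in the e-diary and reports it to the study site instead". A second is withdrawal because of e-diary events. A confirmed Grade 4 event is also entered as an AE.
- **More than one source.** The highest grade from any source is used.
- **Fever.** If a fever is on the AE CRF but "no temperature was captured in the CRF, the fever will be included in the reactogenicity summary with" an unknown temperature range.

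SAP 6.1.1.1.1 and 6.1.1.2.1 report these endpoints by worst grade and cumulatively, by age subgroup and overall. The SAP has no rule converting AE intensity to the Table 7 and 8 bands, no separate row for AE-page grades, and no table restricted to e-diary and unplanned-assessment data.

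**The concern.** For pain, headache, fatigue, chills, muscle pain and joint pain, Grades 1 to 3 of Tables 7 and 8 are themselves functional, so AE intensity is a reasonable stand-in. For redness, swelling, vomiting and diarrhea the two scales measure different things, and the same event can receive different grades depending only on where it was written down.

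Local reactions and systemic events are primary safety endpoints, and severity is how they are broken down. A reader who takes 'severe redness' to have the Table 7 meaning would be wrong for any AE-page record in that row, and could not tell how many there are. Downward errors matter most, because an event that meets the severe cut-off would be absent from a row that is expected to be sparse.

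**Working it through.** The plan states no figure on this point, so there is nothing to reproduce. The check sets the two scales side by side and then sizes the effect of one case.

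**Step 1. Table 7 bands.** One device unit is 0.5 cm, so 4 units = 2.0 cm, 5 = 2.5, 10 = 5.0, 11 = 5.5, 20 = 10.0 and 21 = 10.5 cm. The unit and centimetre bands agree. Redness of 12 cm would be 12 / 0.5 = 24 units, beyond the 21-unit threshold and so Grade 3.

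**Step 2. The same record on each scale** (AE-page-only records, rule applied as written).

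| Record | SAP Table 7 or 8 | AE intensity (Protocol 10.3.3) | Effect of the rule |
|---|---|---|---|
| Redness of 12 cm, function unaffected | Grade 3 | Grade 1 | 2 grades too low |
| Seven loose stools in a day, some interference | Grade 3 | Grade 2 | 1 grade too low |
| One vomiting episode, significant interference | Grade 1 | Grade 3 | 2 grades too high |

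**Step 3. Records in more than one source.** The reported grade is max(e-diary, unplanned assessment, AE page). A maximum cannot fall below the measured grade, so AE intensity can raise it but never lower it. Under-grading therefore needs an event recorded only on the AE page.

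**Step 4. Effect of one re-graded participant.** The shift is 1/N. Group sizes are about 400 (Substudy A) and 300 (Substudy B). The 12-17 cap in Substudy A is 50 in SAP Table 4 and Protocol Table 9. Protocol Table 1 gives 20 instead, so that size is shown too. Intervals are Clopper-Pearson 95%, the SAP's method.

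| N | 0 events | 1 event | Shift (points) |
|---|---|---|---|
| 400 | 0% (0 to 0.92) | 0.25% (0.01 to 1.38) | 0.25 |
| 300 | 0% (0 to 1.22) | 0.33% (0.01 to 1.84) | 0.33 |
| 50 | 0% (0 to 7.11) | 2.0% (0.05 to 10.65) | 2 |
| 20 | 0% (0 to 16.84) | 5.0% (0.13 to 24.87) | 5 |

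The number of affected participants is not in the documents. Taking 1 to 5 in a single row as an assumption, the shift is 0.25 to 1.25 points at N=400, 0.33 to 1.67 at N=300, and 2 to 10 at N=50.

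**The case against.** The case for leaving the rule alone has several sound parts.

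- **It is explicit and prespecified.** The plan does not contradict itself here; the weakness is one of measurement.
- **The route is narrow.** Participants are told to contact the site at once for redness or swelling above 10 cm or any severe systemic event (Protocol 10.7.8.5.1 and 10.8.8.5.1). A 12 cm redness known only from the AE page should be uncommon.
- **AE intensity is not purely functional.** Vomiting that needs IV hydration could reach severe through the treatment wording, so the scales sometimes agree.
- **The fever precedent is imperfect.** Fever is reported in temperature ranges, where an intensity grade has no place. The other events use mild, moderate and severe on both scales.
- **A blunt fix could do harm.** Participants cannot enter Grade 4 in the e-diary, so a flat ban on overriding e-diary grades could suppress a confirmed Grade 4. Nothing shows that the AE page records diameter or stool count, so some investigator-rated severe events could drop out of sight.
- **Timing.** Protocol 2.2.1 already describes Substudy A and B results, so a new grading rule would be post hoc in an open-label study.

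These points limit the size of the problem and shape the remedy. They do not remove the mismatch: an AE-page-only event is still graded on a scale other than the one the table uses.

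**Conclusion.** The point holds for Substudies A and B, and for four events only: redness, swelling, vomiting and diarrhea. AE-page-only records of these can be graded too low or too high by one or two grades; records in several sources can only be graded up. The likely effect is a handful of participants in descriptive tables. No decision rule depends on it, and whether a participant counts as having a reaction is settled by the separate presence rule in SAP Table 6. Sparse severe rows and the 12-17 subgroup are the most sensitive. The sizes rest on the planned enrolment and an assumed number of affected participants.

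A reader might infer more than the documents support:

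- That AE intensity can pull a measured e-diary grade down. The highest-grade rule prevents this.
- That rows captioned with a size or stool count would be mislabelled. No table shells are given; the rows are severity levels.
- That a sore arm raises the grade of a small redness. Intensity is assigned to each AE, and pain is a separate local reaction.
- That the severe rates are materially wrong. No counts are available to show this.
- That Substudy C shares the problem. Its SAP uses a participant-reported reactogenicity CRF and does not contain the AE-intensity rule.

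**What to change.** In SAP 3.1.1.1 and 3.1.1.2 for Substudies A and B:

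1. Grade redness, swelling, vomiting and diarrhea from the AE CRF by Table 7 or 8 whenever the diameter, count or IV hydration is recorded.
2. Otherwise count the event as present and show it in a separate row, 'unknown by Table 7/8', with its AE intensity footnoted or listed so that investigator-rated severe events stay visible.
3. Do not let an AE intensity of Grade 1 to 3 replace a measured e-diary or unplanned-assessment grade. A confirmed Grade 4 always stays Grade 4.
4. Keep AE intensity for pain, headache, fatigue, chills, muscle pain and joint pain.

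If the tables have already been produced, leave them and add either a sensitivity table limited to e-diary and unplanned-assessment data or a footnote giving the source of each grade.

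The cost is a short SAP edit and one extra row. The downside is that some events carry no Table 7 or 8 grade: few if AE-page records are few, but all of them for these four events if the AE page does not capture the measurements.

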The duration (days) of each local reaction will be calculated as the number of days from the start of the first reported reaction to the resolution of the last reported reaction, inclusive (last day of reaction - first day of reaction + 1). Resolution is defined as the last day on which the reaction is recorded in the e-diary or AE CRF if the reaction lasts 7 days or less, or the day the reaction ends if it persists beyond the end of the reactogenicity e-diary period following the study vaccination (the latter will be collected on the symptom resolution or AE CRF). If there is no known date when the reaction ended, then duration will be missing (unknown). Participants with no reported reaction have no duration.

Onset Day

The onset day of each local reaction will be derived. Onset day is defined as the first day of reporting any severity.

For the onset day of each local reaction, if participants report change in severity of the local reaction, only the first day of reporting that specific local reaction will be counted.

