5.3. Methods to Manage Missing Data

In general, completely missing reactogenicity data (ie, all 7 days of collection were missing and no reactogenicity events were reported on the AE CRF) will not be imputed. For partially missing reactogenicity data (eg, 1-6 days of reactogenicity data are available), it is assumed that no reactions or events were experienced on the missing days.

A partial AE start date (missing day or missing both month and day) will be imputed by assigning the earliest possible start date using all available information, such as the stop date of the AE and the study vaccination date(s) from the same participant, following the Pfizer standard for handling an incomplete AE start date. A complete missing start date for an AE is not allowed in the data collection.

Missing serology results will not be imputed. Immunogenicity results that are below the LLOQ will be set to $0.5 \times \text{LLOQ}$ in the analysis; this may be adjusted once additional data on the assay characteristics become available.

No additional imputation will be applied to other missing data.

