6.1.1.1.2. Supplemental Analysis

To support the assessment of local reactions, the following endpoints (as defined in [Section 3.1.1.1](#)) will be summarized with the same analysis time point and analysis population as above, and appropriate analysis methodology and reporting results:

- Duration (days) of each local reaction after the study vaccination.
- Onset day of each local reaction after the study vaccination.

These continuous endpoints will be summarized by displaying n, mean, median, standard deviation, minimum, and maximum by age subgroup (12-17 years, 18-55 years, >55 years) and overall.

Figures:

Bar charts with the proportions of participants for each local reaction throughout 7 days after the study vaccination will be plotted by age subgroup (12-17 years, 18-55 years, >55 years) and overall. The bars will be divided into severity categories to highlight the proportions of participants by maximum severity.

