7.3. Analyses Timing

Statistical analyses will be carried out when the following data are available, for Cohort 1 and Cohort 2 combined and for Cohort 3:

- Safety and immunogenicity data through Visit C4 (1 month after the study vaccination).
- Safety and immunogenicity data through Visit C6 (6 months after the study vaccination).

Additional analyses may be conducted if required for regulatory purposes, to inform product development, and/or for program-level decisions. Certain analyses may be combined as 1 regulatory submission report if the data become available around the same time.

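### Reactions still ongoing at the 1-month cut drop out of the duration summaries, and the Substudies A/B rule can shorten a reaction that outlasts an abandoned diary but ends by Day 7

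*SAP*

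**What the plan says.** Both SAPs compute duration in section 3.1.1.1 as last day minus first day plus one, and section 3.1.1.2 applies the same derivation to systemic events. For an unrecorded end the rule is "If there is no known date when the reaction ended, then duration will be missing (unknown". Section 5.3 of each SAP rules out a substitute value: "No additional imputation will be applied to other missing data". The duration tables (sections 6.1.1.1.2 and 6.1.1.2.2 of each SAP) are simple: "These continuous endpoints will be summarized by displaying n, mean, median, standard deviation, minimum, and maximum by age subgroup". Neither SAP mentions censoring, a lower bound or a count of reactions still ongoing.

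The first analysis is at 1 month. Section 7.3 of the Substudy C SAP lists "Safety and immunogenicity data through Visit C4 (1 month after the study vaccination"; section 7.3 of the A/B SAP sets the matching cut at Visit 3. Both plan a second analysis at 6 months.

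The SAPs differ on where the end date comes from. In the A/B SAP, resolution is the last day "recorded in the e-diary or AE CRF if the reaction lasts 7 days or less", and otherwise "the day the reaction ends if it persists beyond the end of the reactogenicity e-diary period following the study vaccination". The symptom-resolution CRF is named only for that second case. The Substudy C SAP instead takes the latest end date whenever a reaction appears in several sources. For diary days left blank, both SAPs say in section 5.3 that "it is assumed that no reactions or events were experienced on the missing days".

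For Substudies A and B, protocol section 8.3.4 says site staff "must obtain stop dates from the participant for any ongoing local reactions, systemic events, or use of antipyretic medication on the last day" on which the diary was filled in. The 1-week and 1-month visit procedures repeat this (10.7.8.5.2 and 10.7.8.5.3; 10.8.8.5.2 and 10.8.8.5.3).

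**The concern.** There are two separate problems.

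First, a reaction that has not ended by the data cut has no end date and so no duration. It is left out because it is long, which means the exclusion depends on the quantity being measured. The n, mean and maximum then describe only reactions whose end is known, and the table does not say how many were ongoing.

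Second, the protocol for Substudies A and B collects a stop date for anything present on the last completed diary day, whichever day that was. The A/B SAP uses that date only for reactions running past the diary period. For a shorter reaction whose diary was abandoned, the literal rule stops the clock at the last entry.

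At stake is the description of how long reactions last. The most persistent ones are what a reader would look for in a duration table.

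**Working it through.** The documents state no duration figure, so there is nothing to reproduce. The rules can be applied to worked cases and the possible bias expressed as a formula.

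**1. Length of a reaction still ongoing at 1 month.** Visits A3, B3 and C4 fall 28 to 35 days after vaccination (protocol schedules of activities). Vaccination is Day 1, so these are study Days 29 to 36. Minimum length = visit day − onset day + 1, with onset on Days 1 to 7:

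- Day 29 visit: 29 − 7 + 1 = 23 days (onset Day 7); 29 − 1 + 1 = 29 days (onset Day 1).
- Day 36 visit: 36 − 7 + 1 = 30 days (onset Day 7); 36 − 1 + 1 = 36 days (onset Day 1).

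Such a reaction has therefore lasted at least 23 to 36 days, and the rule records it as missing.

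**2. Effect on the mean.** Let m be the mean of the reactions kept, f the fraction dropped and L their length so far. The full mean is at least (1 − f)m + fL, so the understatement is at least f(L − m). The documents give neither f nor m. Assuming m = 2 days:

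| f | L = 23 | L = 36 |
|---|---|---|
| 0 | 0 | 0 |
| 0.5% | 0.005 × 21 = 0.105 | 0.005 × 34 = 0.17 |
| 1% | 0.01 × 21 = 0.21 | 0.01 × 34 = 0.34 |
| 2% | 0.02 × 21 = 0.42 | 0.02 × 34 = 0.68 |
| 5% | 0.05 × 21 = 1.05 | 0.05 × 34 = 1.70 |

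The assumed m matters little: at f = 1%, m = 1.5 with L = 23 gives 0.01 × 21.5 = 0.215 days, and m = 3 with L = 36 gives 0.01 × 33 = 0.33 days. A single dropped case lowers the maximum if it is longer than the longest reaction kept. The median moves little when such cases are few.

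**3. The A/B end-date rule, read literally.** Onset is Day 1, the reaction is present on the last diary day, and no AE CRF entry covers the later days. The two branches are taken to divide at Day 7, the end of the diary period.

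| Diary stopped | Reaction ended | Stop date held | True length | A/B SAP length |
|---|---|---|---|---|
| Day 3 | Day 6 | yes | 6 | 3 |
| Day 2 | Day 7 | yes | 7 | 2 |
| Day 1 | Day 7 | yes | 7 | 1 |
| Day 3 | Day 10 | yes | 10 | 10 |
| Day 3 | Day 10 | no | 10 | missing, or 3 if read from the diary |

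The loss is 1 day at the least (diary stopped Day 6, ended Day 7: 7 − 6) and 6 days at the most (7 − 1). If a fraction g of reactions were cut by d days, the mean would fall by g × d: from 0.01 × 1 = 0.01 to 0.10 × 6 = 0.60 days for g between 1% and 10%. These values of g are assumptions too.

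**The case against.** A reader might infer that the A/B SAP shortens every reaction that outlasts an abandoned diary. The documents do not support that. A reaction running past Day 7 takes its collected stop date and keeps its full length (10 days stays 10). The loss is confined to reactions ending by Day 7. With no stop date, the SAP does not say which branch applies. Even for the short reactions, AE CRF entries count as a source, and protocol section 8.3.4 sends events missed in the diary but reported to the site to the AE page. An AE entry covering the later days would prevent the loss; whether sites would make one for a reaction already in the diary is arguable.

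A reader might also infer that every missing duration is a long one. An unknown end date also covers reactions that resolved on an unrecorded day, and these need not be long. The downward direction is certain only for reactions truly ongoing.

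The 6-month analysis may recover durations once a stop date is entered. That is a fair point, particularly for Substudy C, where follow-up continues until resolution (protocol section 8.3.5). It is less assured in A and B, whose schedules list obtaining stop dates only at the 1-week and 1-month visits. In any case the 1-month tables would already have been produced.

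Finally, the shortfall can be partly derived by setting n for duration against the count of participants with the reaction. That shows how many durations are missing, but does not separate ongoing reactions from unrecorded ends.

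**Conclusion.** The point holds in limited form and is minor. In both SAPs, reactions truly ongoing at the 1-month cut are removed because they are long, which biases the reported mean and maximum downward. In the A/B SAP, reactions that outlast an abandoned diary but end by Day 7 can be shortened by 1 to 6 days, on a literal reading and absent an AE CRF entry.

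The size is unknown and could be nil. Every figure above for the mean rests on assumed fractions and an assumed typical duration; the 23-to-36-day lower bound rests only on the visit windows and onset on Days 1 to 7.

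It would be tempting to conclude that the primary tolerability result is biased. It is not affected by this rule: the primary estimand is the percentage of participants reporting each reaction, duration is listed only as a supplemental summary, and no decision rule uses it.

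**What to change.** 1. In the A/B SAP, section 3.1.1.1, define the end date as the latest of the e-diary, the symptom-resolution CRF and the AE CRF for reactions of any length. The Substudy C SAP already takes the latest date across sources.
2. In both SAPs, report for each local reaction and systemic event, beside n, the number ongoing at the cut and, separately, the number with an unknown end date. Show ongoing reactions in the maximum as *at least X days*, with X counted to the last date the reaction was known to be present.

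A censored-data (Kaplan-Meier) median is optional: it is a preference for a supplemental table, and it assumes that censoring is unrelated to how long the reaction lasts.

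The cost is a few sentences, one derivation change and extra table columns; stated durations become slightly longer. Stop dates are already collected. The documents do not specify a field for the last date known present after the diary ends, so X may have to come from the last diary entry or site contact that recorded the symptom. Protocol section 2.2.1 already describes 1-month immunogenicity results for Substudies A and B. If the 1-month duration tables have also been reported, the A/B change should be labelled post hoc.
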